3.5.1 Preliminary work – Feasibility Trials

There have been two feasibility trials (led by [name] in the UK and Wald in Canada) comparing an intensive versus liberalised phosphate control strategies in ESKD patients (Table 3.3)²⁴⁻²⁶. These studies importantly demonstrated that it is feasible to enrol dialysis patients in phosphate target trials; and achieve and maintain separation of serum phosphate levels between the two trial arms.

Table 3.3. Summary of two phosphate target feasibility trials in ESKD patients

	TARGET ²⁴	SPIRIT ^{25, 26}
Setting	6 centres in Canada	2 centres in the UK
Total participants	104	104
Study population	Age>18 yrs, haemodialysis >3mo	Age>30 yrs, any dialysis > 6mo
Follow-up	26 weeks	13 months

Phosphate-lowering medications	Only calcium carbonate	Sevelamer, lanthanum
Intensive PO ₄ control/ achieved level	0.75 – 1.50 mmol/L Mean ± SD 1.46 ± 0.36	0.80 – 1.40 mmol/L Mean ± SD 1.64 ± 0.4
Liberalised PO ₄ control/ achieved level	2.00 – 2.50 mmol/L Mean ± SD 1.95 ± 0.45	1.80 – 2.40 mmol/L Mean ± SD 2.00 ± 0.4
Achieved difference in PO ₄	0.47 mmol/L (95%CI 0.36 to 0.56)	Mean difference >0.32 mmol/L

The PHOSPHATE Study builds on evidence from these two feasibility trials and has evolved into a large global collaborative trial with clinical endpoints. In addition, a feasibility survey in Australia across 33 renal units demonstrated strong support with 97% of sites were interested to participate in a multi-centre trial and to recruit a minimum of 20 participants. In New Zealand, eight renal units indicated support to recruit 100 participants. The PHOSPHATE trial will be conducted simultaneously in Australia, New Zealand, Canada and the UK.

4. STUDY HYPOTHESIS AND OBJECTIVES

4.1 Study hypothesis

Compared to a strategy of liberalised phosphate control, intensive phosphate lowering aimed at normalisation (≤ 1.50 mmol/L) reduces the risk of fatal or non-fatal major cardiovascular events in ESKD patients receiving dialysis.

4.2 Study objectives

4.2.1 Primary objectives

To test the hypothesis that, compared to a strategy of liberalised phosphate control, intensive phosphate-lowering aimed at reduction of serum phosphate concentration towards the normal level (≤ 1.50 mmol/L) reduces the risk of fatal or non-fatal major cardiovascular events in ESKD patients receiving dialysis. This hypothesis will be tested using a composite outcome including cardiovascular death, non-fatal myocardial infarction, coronary revascularisation, non-fatal stroke, and peripheral arterial event (revascularisation or amputation).

4.2.2 Secondary objectives

The trial will examine the effect of intensive reduction of serum phosphate level on all-cause mortality, individual components of the composite outcome, all-cause hospitalisation, and utility-based quality of life.

5. TRIAL DESIGN

5.1 Overall study design

The PHOSPHATE Study is an investigator-initiated, international, multi-centre, prospective, randomised, open-label, parallel-group, superiority, and pragmatic large simple trial (LST). A total of 3600 adult participants on phosphate-lowering

medications will be recruited from the participating renal units from Australia, New Zealand, Canada and the UK.

The participants will be randomised to either an intensive phosphate control - phosphate-lowering treatments aimed to intensively lower serum phosphate concentration towards normal level (≤ 1.50 mmol/L) or to a strategy of liberalised phosphate control - which will be achieved by discontinuation of all phosphate-lowering medications and commencing phosphate-lowering treatments only if serum phosphate concentration exceeds 2.50 mmol/L.

5.2 Study population

5.2.1 Inclusion Criteria

To be eligible to participate in this trial, participants need to satisfy ALL of these inclusion criteria:

1. Age ≥ 45 years, or Age ≥ 18 years with diabetes,
2. ESKD treated with haemodialysis or peritoneal dialysis, for at least 3 months,
3. Prescribed at least one phosphate-lowering medication at any dose.
4. Able to provide informed consent

5.2.2 Exclusion Criteria

Potential participants must have NONE of the following exclusion criteria:

1. Elective kidney transplantation scheduled within the next 6 months,
2. Concomitant major illness / comorbidity likely to result in death in the next 6 months in the view of the treating physician,
3. Participation in an interventional study that is likely to affect serum phosphate concentration.

5.2.3 Screening log

A screening log that lists all patients evaluated or considered for enrolment in the PHOSPHATE Study will be completed by trial study staff at each study site. The log will record all screened patients, whether or not they are enrolled into the study. For each patient considered for study entry the screening log will record if the patient was randomised, or the reason they were not enrolled. For example, the reasons for ineligibility (not meeting specific inclusion criteria; meeting one or more exclusion criteria) or the reasons for eligible patients not being enrolled in the study (e.g. patient refusal) will be recorded.

5.3 Comparators

5.3.1 Experimental intervention: Intensive phosphate control (≤ 1.50 mmol/L)

The intensive serum phosphate control (≤ 1.50 mmol/L) will be achieved by the treating physician by using phosphate-lowering treatments (including dietary phosphate restriction, phosphate-lowering medications, and optimisation of dialysis regimen) aimed to intensively lower serum phosphate concentration towards normal level (≤ 1.50 mmol/L).

Since the phosphate concentration in this group is the same as that recommended by the KDIGO Guidelines (<1.50 mmol/L), this group represents the contemporary standard of care. Treating nephrologists or site investigators will be allowed to prescribe phosphate-lowering medications of their choice or local availability.

5.3.2 Control intervention: Strategy of liberalised phosphate control

All phosphate-lowering medications will be discontinued. Phosphate-lowering treatments (including dietary phosphate restriction, phosphate-lowering medications, and optimisation of dialysis regimen) will be commenced only if serum phosphate concentration exceeds 2.50 mmol/L. Treating physicians will be allowed to use phosphate-lowering medications of their choice and local availability to keep serum phosphate levels below 2.50 mmol/L and these medications will be discontinued if serum phosphate falls to 2.00 mmol/L or lower.

Justification for not mandating specific phosphate-lowering medications

The PHOSPHATE Study is testing two treatment strategies around phosphate lowering and is not testing specific phosphate-lowering medications. The choice of phosphate-lowering medication, if one is needed, will be at the discretion of clinicians.

This approach is similar to that of the Systolic Blood Pressure Intervention Trial (SPRINT), which compared the benefit of treatment of intensive blood pressure control (systolic blood pressure <120 mm Hg: experimental group) with less intensive blood pressure control (systolic blood pressure <140 mm Hg: control group)²⁷. The SPRINT was designed to compare strategies of intensive vs. less intensive systolic blood pressure control without mandating specific antihypertensive classes or agents to reach the treatment goal. Clinicians were allowed to use a wide array of drugs from multiple antihypertensive classes to achieve these blood pressure targets. Similar to the SPRINT, participants in the intensive phosphate control group are likely to receive phosphate-lowering medications as a single agent or in combinations. The network meta-analysis conducted by Palmer and colleagues showed that there were no statistical differences in all-cause or cardiovascular mortality risks between different phosphate-lowering medications. Therefore, treating nephrologists or site investigators will be allowed to prescribe phosphate-lowering medications of their choice or local availability instead of mandating specific phosphate-lowering medications.

5.3.3 Concurrent management

Dietary advice

All participants in the trial will receive dietary advice according to the usual standard of care and local practice. However, in the liberalised phosphate control group, advice specifically related to dietary phosphate restriction will be omitted unless the serum phosphate concentration exceeds 2.50 mmol/L.

Usual care

Other than the allocated trial intervention, all other aspects of care provided to participants will follow usual local practice. All participants will receive their usual

ESKD management as per local standard of care, including, but not limited to dialysis modality/regimen/access, dietary advice/intervention, transplant planning and management of target serum calcium and parathyroid hormone concentrations, malnutrition, hypertension, anaemia, oedema, and cardiovascular risk factors and disease. Patients can be dialysed in any setting (home, facility, community-house, home assisted, satellite).

5.3.4 Discontinuation/modification of trial phosphate strategy

The trial phosphate strategy may be temporarily or permanently discontinued in any of the following situations:

- serious adverse event thought likely due to the trial phosphate strategy ,
- pregnancy or condition where continuation of the trial phosphate strategy is not in the participant's best interests (e.g. adoption of palliative/conservative care),
- at participant's or treating physician's request.

Even if the trial phosphate control strategy to which the participant has been allocated has been modified or discontinued, the participant **should remain** in the trial and be followed until the end of study, (except where the participant withdraws consent to participate in the study) and analyses will be conducted using an intention-to-treat principle. More information on early withdrawal from the study is described in section 5.6.

5.3.5 Adherence to intervention

Monitoring of the serum phosphate concentration will be according to the usual standard of care at dialysis units. No additional serum phosphate monitoring will be required for trial conduct. Patients will be contacted via phone or in-person to change phosphate-lowering medication depending on the arm to which they are allocated

5.4 Randomisation

Participants will be randomised in a 1:1 ratio via a web-based randomisation system embedded within a trial database administered by the AKTN (Australian, New Zealand, and Canadian centres) or the Cambridge Clinical Trials Unit (UK centres). The systems will be accessible by centre staff via a password-protected encrypted website interface. Randomisation will be stratified by centre and use random permuted blocks to ensure similar numbers of participants in the two intervention groups at each centre.

5.5 Blinding

5.5.1 Who will be blinded after assignment to interventions

Due to the nature of the trial interventions, participants, treating nephrologists and investigators will not be blinded. Outcome assessors, including trial statisticians and principal investigators will remain blinded.

5.6 Duration of follow up and early withdrawal from the study

All participants enrolled in the study will be followed until a total of 1,190 study endpoints have occurred. The planned follow-up for the study is unlikely to exceed 5 years from recruitment of the first participant. A participant may be withdrawn from the study earlier in any of the following situations:

- withdrawal of consent to remain in the trial,
- transfer to another renal unit which is not an active study site,
- loss to follow up

Permanent cessation of trial phosphate target does not constitute participant withdrawal. If the trial phosphate strategy is stopped permanently for any reason, the participant is to continue participating and data collection will continue until the final study follow-up time point. If a participant expresses a wish not to complete questionnaires, they should remain in the study and other trial-related data will be obtained from medical records review, and/or other treating physicians. Every effort will be made to determine each participant's status on the components of the primary outcome. Consent forms at study entry will also include consent to data linkage and all other legal means to determine survival status. The integrity and validity of the study relies on following up randomised participants until the target number of primary outcome events has occurred.

5.7 Outcome measures

5.7.1 Primary outcome measure

Time to a composite endpoint of the following events:

1. Cardiovascular death
2. Non-fatal myocardial infarction
3. Coronary revascularisation
4. Stroke
5. Peripheral arterial event

5.7.2 Secondary outcome measures

1. Individual components of the primary composite endpoint (cardiovascular death, non-fatal myocardial infarction, coronary revascularisation, non-fatal stroke and peripheral arterial event)
2. Time to all-cause death
3. All-cause hospitalisation
4. Quality of life measured using EQ-5D-5L

6. TRIAL PROCEDURES

6.1 Recruitment of participants

Participants will be recruited from renal units that provide a comprehensive nephrology service in Australia, New Zealand, Canada and the UK. Participants must meet the study inclusion criteria and not meet any exclusion criteria.

6.2 Patient consent

Patient consent forms will be approved by the responsible Independent Ethics Committee (IEC) for each participating site prior to the beginning of the trial at the site. A copy of the final approved version will also be filed with the regional coordinating centre, following approval from the IEC and governance office.

If the participant is unable to read the PICF, an impartial witness will be present during the entire discussion and will also be responsible for signing and dating the form on the participants' behalf if he or she is unable to write in English or in the same language used in the consent form. In doing so, the witness attests that the information that was explained to the participant was accurately represented on the consent form and that it was apparently understood by the participant, and that informed consent was freely given by the participant.

After discussing the trial, ample time will be given to the participant, accompanying person or legal representative to enquire about the trial and decide whether to participate. No person involved with the trial will coerce or unduly influence the decision to participate in a trial.

A copy of the signed consent form and the patient information sheet will be supplied to the participant. The original signed consent forms will be filed in the Site Trial Master File, and a copy placed in the patient's hospital medical record as required.

Patient consent must be obtained prior to the randomisation or initiation of any trial procedures, including screening tests to confirm eligibility. Patients will not be randomised until a signed consent form is filed at site.

The Global Trial Management Committee will continue to review the medical literature, and any other relevant information impacting on the continuation of the trial. Consent forms and patient information sheets will be revised should any relevant and important new information become available, and resubmitted for site IEC approval.

6.3 Screening and randomisation

Screening of the potential participants will occur during their usual visit to their treating physician or through the study site's integrated patient database. The potential participant will have an initial consultation with a renal physician to discuss study participation. This will include a preliminary eligibility check.

Randomisation must occur only after obtaining informed consent. Randomisation must occur within one month of obtaining informed consent. This will include a check to ensure that the patient is still eligible.

6.4 Study visits schedule

There will be no designated study visits. All participants will be assessed by their treating nephrologists at 1-3 monthly intervals based on the local standard practice.

6.4.1 Trial-specific investigations

There will be no trial-specific laboratory or radiological investigations. Any investigations will be performed per usual clinical indication. All trial-related titration of phosphate-lowering medications will be based on blood tests that are part of standard dialysis care.

6.5 *Data Collection schedule*

Data collection will be kept to a minimum and focus on baseline data, data for endpoint ascertainment and monitoring separation of serum phosphate levels (Table 6.1). Individual countries may collect additional data (refer to Country Specific Appendices for further details)

Table 6.1 Global Study Data Collection Schedule

Data Collection Timing	Screening	Baseline	3 Monthly	6 Monthly	End of Study
Inclusion/ exclusion criteria	X				
Informed Consent	X				
Randomisation		X			
Demographics		X			
Medical history		X			
Key concomitant medications		X			
Serum phosphate level*		X	X		X
Primary endpoints			X		X
All-cause death			X		X
All-cause hospitalisation			X		X
EQ-5D-5L		X		X	

*A maximum of 3 phosphate results will be entered, at least 4 weeks apart

6.6 Clinical assessment

6.6.1 Baseline demographic characteristics

Date of birth

Sex

Height and weight

Race/Ethnicity

Medical history (diabetes mellitus, myocardial infarction, coronary artery disease, heart failure, stroke, peripheral arterial disease, cancer, parathyroidectomy, calciphylaxis)

Primary cause of kidney disease

Smoking history

Key concomitant medication – phosphate-lowering medication, calcium, nutritional vitamin D, active vitamin D (calcitriol), cinacalcet.

6.6.2 Laboratory procedures and investigations

Local laboratory

The frequency of monitoring of serum phosphate concentration will be according to the usual local standard of care. All dialysis centres monitor serum phosphate concentrations every 1-3 monthly as standard practice. No additional serum phosphate monitoring is required.

Quality of Life

Information on quality of life will be collected using the generic health status instrument, the EQ-5D-5L, at baseline and 6 monthly for at least 2 years.

6.7 Assessment of safety

6.7.1 Definitions

Serious Adverse Event (SAE)

An adverse event (any untoward medical event, see below) is classified as SERIOUS (SAE) if it meets any one of the following criteria:

- Death
- Life-Threatening: The subject/participant was at substantial risk of dying at the time of the adverse event or it is suspected that the use or continued use of the product would result in the subject's/participant's death.
- Hospitalisation (initial or prolonged): Requires admission to the hospital (for 24 hours or more) or prolongation of a hospital stay.
- Disability: Resulted in a significant, persistent, or permanent change, impairment, damage or disruption in the subject's/participant's body function/structure, physical activities or quality of life.
- Congenital Anomaly/Birth Defect
- Important medical events: Other medically important events that, in the opinion of the investigator, may jeopardise the subject/participant or may require intervention to prevent one of the other outcomes listed above.

Suspected Unexpected Serious Adverse Reaction (SUSAR)

A SUSAR is an adverse event related to an investigational medicinal product that results in death of subject/participant or is life-threatening/disabling AND is unexpected or unanticipated.

6.7.2 Study specific reportable adverse events

Adverse events will be managed as per usual local clinical care practice.

Events that are already being collected as part of the study primary or secondary outcomes will be reported as study endpoints and not as Serious Adverse Events.

Events that are not study endpoints and meet the criteria for an SAE will be reported if judged, in the opinion of the site investigator, possibly or probably related to the randomised phosphate target. SAEs judged not or unlikely related to the randomised phosphate strategy will not be reported because these events are not informative in determining the safety of the study intervention. All events related to adverse pregnancy outcomes, and any congenital anomaly or birth defects will be reported, whether related to randomised phosphate target or not.

Since side effects of all available phosphate-lowering medications that are approved and used widely in clinical practice are well known, ADRs of individual phosphate-lowering medications will not be recorded.

6.7.3 Period of Observation

For the purposes of this study, the period of observation for collection of treatment-related serious adverse events will be from the time of randomisation until the participant's end-of-study visit.

7. STATISTICAL CONSIDERATIONS

7.1 Sample size calculation

A sample size of 3,564 participants was calculated on the basis of the following assumptions: an annual rate of the primary outcome of 13% in the liberalised phosphate control group, a three year recruitment period, a five year total study duration, and 1% loss to follow-up. A two-sided log-rank test with an overall sample size of 3,564 participants has 80% power at the 5% significance level to detect a hazard ratio (HR) of 0.85 (a 15% intervention effect). The overall number of primary outcome events required is 1,190. A sample size of 3,564 participants has more than 90% power to detect a larger 20% intervention effect (HR 0.80). Therefore, the trial aims to enrol 3,600 participants.

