All participants will be assessed by their treating nephrologists at 1-3 monthly intervals, which is the standard practice. This is an event-driven trial, and the trial will continue until a total of 1,190 primary endpoint events have occurred. The planned follow-up for the study is unlikely to exceed 5 years from recruitment of the first participant. Participants may be withdrawn from the study earlier if they transfer to another dialysis unit which is not an active study site, or withdraw consent.

Figure 2.1: The study schema

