3.1 Outcomes in ESKD patients receiving dialysis

Over three million people worldwide are currently living with ESKD and require renal replacement therapy^{3, 4}. The need for dialysis is projected to double globally by 2030. Although dialysis is a life-sustaining therapy, the death rate among ESKD patients receiving dialysis is unacceptably high at 13 per 100 person-years⁵. Despite the annual cost of more than \$34 billion in United States alone⁶, the age-adjusted mortality rates of dialysis patients is 10 to 100 times higher than that of the general population^{7, 8}. Furthermore, ESKD patients suffer from impaired taste, loss of appetite, malnutrition, and poor quality of life.⁹

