7.2 Statistical analysis

The intervention effect for the primary composite outcome will be illustrated by Kaplan–Meier product-limit estimates of the event-free survival time and analysed using a two-sided log-rank test stratified by country (Australia, Canada, New Zealand, and UK). Hazard ratios and corresponding 95% confidence intervals for the intervention effect adjusted for country will be calculated from a Cox proportional-hazards regression model. Intervention group differences according to major subgroups at randomisation (age, gender, country, race, diabetes, cardiovascular disease, time on dialysis) will be examined in Cox regression models incorporating an intervention group by subgroup variable interaction. The intervention effect for time-to-event secondary outcomes will be analysed using the same methods. Intervention groups will be compared on quality of life (EQ-5D-5L) scores using a linear mixed model. If there is substantial censoring due to transplantation and/or death, a joint modelling approach will be used accommodate the informative dropout.

Interim analyses on the primary outcome will be conducted using O'Brien-Fleming boundaries. There will be three interims and a final analysis. The interim analyses will be done when approximately 25%, 50% and 75% of the required events have occurred.

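### Section 7.1 makes no allowance for non-cardiovascular death, so the stated 5-year duration is probably too short by about 0.2 to 0.8 years for 1,190 events

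*Protocol*

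**What the plan says.** Section 7.1 assumes "an annual rate of the primary outcome of 13% in the liberalised phosphate control group", together with "a three year recruitment period, a five year total study duration, and 1% loss to follow-up". From this it claims, for 3,564 participants, "80% power at the 5% significance level to detect a hazard ratio (HR) of 0.85", and adds: "The overall number of primary outcome events required is 1,190". Enrolment is then rounded up to 3,600.

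The primary composite (synopsis, section 5.7.1) includes cardiovascular death but not death from other causes. Section 3.1 states that "the death rate among ESKD patients receiving dialysis is unacceptably high at 13 per 100 person-years". Section 7.2 allows for the possibility that transplantation and death cause substantial censoring, but only when it describes the analysis of quality of life.

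On duration, the synopsis gives 5 years and also follow-up to 1,190 endpoints. Sections 2 and 5.6 make the trial event-driven and add: "The planned follow-up for the study is unlikely to exceed 5 years from recruitment of the first participant". Section 7.2 also plans sequential monitoring with O'Brien-Fleming boundaries: "There will be three interims and a final analysis".

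**The concern.** Non-cardiovascular death is a competing event: it ends follow-up for the primary outcome without contributing to the count. In a dialysis population with the mortality quoted in section 3.1, it could remove far more people than 1% loss per year does. If the calculation leaves it out, events arrive more slowly than projected. The statements about 5 years in the synopsis and in sections 2, 5.6 and 7.1 are then too optimistic. If the trial were nevertheless closed at 5 years, it would have fewer events than its stated power needs.

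**Working it through.** **Inputs from the protocol.** Control hazard 0.13 per year; HR 0.85, so intensive hazard 0.1105; 1:1 allocation; 3-year recruitment (taken as uniform); 5 years in total; loss 0.01 per year; two-sided 5%; 80% power.

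**Step 1: required events (Schoenfeld, fixed design).** 4 × (1.960 + 0.842)² / (ln 0.85)² = 1,188.7. At 1,190 events the power is 80.0%.

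**Step 2: reproduce 3,564.** Let m be the non-cardiovascular death hazard and k = λ + 0.01 + m. With follow-up uniform between 2 and 5 years, the chance of an observed primary event is

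P(λ) = (λ/k) × [1 − (e^(−2k) − e^(−5k)) / (3k)].

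With m = 0:
- control, k = 0.14: P = 0.3555
- intensive, k = 0.1205: P = 0.3123
- events = 1,782 × (0.35551 + 0.31227) = 1,189.98

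This is the stated 1,190. Other readings do not reproduce the pair of figures: 1,190 events would need 3,504 participants with no loss, or about 3,514 with 1% loss in total over 5 years. Reading 13% as an annual risk (hazard 0.139) gives 1,257 events from 3,564. The stated design therefore has m = 0.

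**Step 3: margin from rounding up.** With 3,600 enrolled and m = 0, 1,202 events are expected at 5 years and the 1,190th at 4.96 years. Solving for the m that gives exactly 1,190 events at 5 years yields about 0.006, or 0.6 per 100 person-years. Against an all-cause rate of 13, that is 0.6/13 = 4.6%, so more than 95% of deaths would have to be cardiovascular.

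**Step 4: add non-cardiovascular death.** The protocol gives no rate for this, so m is an assumption. The value 2.9 is the difference between the median all-cause (3.0) and cardiovascular (0.1) rates in the earlier trials that section 3.4.1 calls low-risk; it is a rough low end, since it subtracts two medians. The values 4, 6.5 and 9.1 are about 30%, 50% and 70% of 13. With 3,600 enrolled:

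| m per 100 person-years | Events at 5 years | Power if closed at 5 years | 1,190th event (years) | 1,217th event (years) |
|---|---|---|---|---|
| 2.9 | 1,145 | 78.5% | 5.2 | 5.3 |
| 4 | 1,125 | 77.8% | 5.3 | 5.4 |
| 6.5 | 1,080 | 76.1% | 5.5 | 5.7 |
| 9.1 | 1,037 | 74.4% | 5.8 | 6.0 |

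For example, at 6.5 the two probabilities are 0.3198 and 0.2804, and 1,800 × 0.6002 = 1,080. Power is Φ(√1,080/2 × 0.1625 − 1.960), about 76%. All powers in the table are fixed-design.

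**Step 5: interim looks (minor).** Four O'Brien-Fleming analyses at two-sided 5% have a final critical value of about 2.024 and an inflation factor of about 1.024. For 80% power, 1,188.7 × 1.024 = 1,217 events are needed; 1,190 events give about 79%. The last column of the table gives the matching durations.

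**The case against.** **Power is protected.** A reader might infer that the trial has only about 76% power. The documents do not support that. Follow-up runs until 1,190 events, no section sets a calendar stop at 5 years, and 5 years is worded as a limit unlikely to be exceeded. Slower accrual of events delays the end and leaves fixed-design power at about 80%. The interims are tied to event fractions, so their information content does not change either. This objection stands, and it reduces the point mainly to a duration that is understated.

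**The size is not fixed by the protocol.** It is tempting to say that 76% and 5.5 years follow from the protocol's own mortality. They do not: the figure of 13 is all-cause, has no cardiovascular split, and describes dialysis patients in general. The trial excludes people likely to die within 6 months, so its rate may be lower. This stands too, and only a range can be given. The direction survives, because the threshold is as low as 0.6 per 100 person-years.

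**Other inputs matter as much.** At 6.5 per 100, a control hazard of about 0.147 instead of 0.13 would restore 1,190 events at 5 years. If 13% were meant as an annual risk, the 6.5 case would give 78.4% power at 5 years, but that reading does not reproduce 3,564. If the treatment had no effect, the 1,190th event in the 6.5 case would come at 5.17 years, which is still late. These points argue for stating a range rather than one figure. They do not justify leaving the competing risk at zero.

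**Conclusion.** The point holds as a planning error of moderate severity. Section 7.1 removes nobody through non-cardiovascular death, so 1,190 events and 80% power at 5 years would not be reached at any plausible rate of such death under its other assumptions. Under an assumed 2.9 to 9.1 per 100 person-years with 3,600 enrolled, the duration is understated by about 0.2 to 0.8 years. Power drops to about 74% to 79% only if the trial closes at 5 years.

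The figures rest on constant, independent hazards, the same non-cardiovascular death rate in both arms, uniform accrual and HR 0.85. Removal through transplantation or transfer to a non-participating unit is left out, because the protocol gives no rate; it would push in the same direction. The test, event target and type I error are not affected. The interim-look shortfall of about one percentage point is a minor addition.

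**What to change.** Redo section 7.1 with an explicit, stated non-cardiovascular death hazard in addition to the 1% annual loss, and show a range around it. Then do one of two things:

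- restate the duration in the synopsis and in sections 2, 5.6 and 7.1, at about 5.2 to 5.8 years for 1,190 events, depending on the rate chosen; or
- if the trial is to close at 5 years, state the lower power that goes with the chosen rate.

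In the same edit, either say that 1,190 events give about 79% power with the three interim looks, or adopt about 1,217 events with their own durations (about 5.3 to 6.0 years; 5.7 at 6.5 per 100). The durations for 1,190 events should not be paired with the 1,217 target.

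The cost is protocol wording and a slightly less favourable stated duration or power. Any longer follow-up is already implied by the event-driven design, and enrolment stays at 3,600.
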